Participants and setting. The study will test 30 current cocaine users (enroll 45 to complete 30), 19 to 55 years old, who meet current DSM-5 criteria for cocaine use disorder (CUD) of at least moderate severity (≥ 4 symptoms). Subjects meeting criteria for substance use disorders other than cocaine, marijuana, or nicotine will be excluded. Notably, because the study medication (suvorexant) is contraindicated with alcohol use, we will exclude subjects with alcohol use disorders (via screening at intake). We will also exclude those individuals who are drinking > 10 alcoholic drinks per week (NIAAA criteria problem drinking = at least 14 drinks per week), and who are unwilling to stop using alcohol in the evening for the two weeks of the study. We will exclude those who report binge drinking (NIAAA criteria = in < 2.5 hours, 5 drinks for men, 4 drinks for women).

Other exclusion criteria will include significant and unstable medical/ psychiatric disorders which might make participation hazardous; acute or chronic health conditions; and concomitant medication use contraindicated with the study medication (suvorexant). This will be accomplished via full medical evaluation at intake by [name], M.D., CNRA Medical Director. The study will be conducted at the Neurobehavioral Research Laboratory at the CNRA, directed by [name]. Recruitment strategies will include local advertising in print media, public service announcements on radio, and referrals to CNRA in the Houston metropolitan area. Based on previous and current CNRA recruitment rates of participants with CUD, we expect to enroll 3-4 participants per month to meet recruitment goals.

Measurements

Cue reactivity: Attention bias (AB) task is a saccade-based eye-tracking measurement, developed by [name] to assess attentional bias to drug cues⁴⁸. Eye movements (saccades) have advantages over other variables because they are directly observable, ecologically valid, and typically stable across repeated measures^{49,50}. AB measures utilizing eye movements have produced moderate to robust effects for a broad class abused substances⁵¹⁻⁵³, including cocaine^{34,48,54}. Using our drug specific anti-saccade task, the between-group effect size for anti-saccade error rates in the presence of cocaine cues was large: CUD vs. control Cohen's $d_{av} = 0.6$ ⁴⁸.

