The study will test 30 current cocaine users (enroll 45 to complete 30), 19 to 55 years old, who meet current DSM-5 criteria for cocaine use disorder (CUD) of at least moderate severity (≥ 4 symptoms). Subjects meeting criteria for substance use disorders other than cocaine, marijuana, or nicotine will be excluded. Notably, because the study medication (suvorexant) is contraindicated with alcohol use, we will exclude subjects with alcohol use disorders (via screening at intake). We will also exclude those individuals who are drinking > 7 alcoholic drinks per week, and who are unwilling to stop using alcohol in the evening for the two weeks of the study. Other exclusion criteria will include significant and unstable medical/ psychiatric disorders which might make participation hazardous; acute or chronic health conditions; and concomitant medication use contraindicated with suvorexant (e.g., medications with sedative properties). This will be accomplished via full medical evaluation at intake by [name], M.D., CNRA Medical Director. The study will be conducted at the Neurobehavioral Research Laboratory at the CNRA, directed by [name]. Recruitment strategies will include local advertising in print media, public service announcements on radio, and referrals to CNRA in the Houston metropolitan area. Based on previous and current recruitment rates of cocaine treatment-seeking men and women for studies at the CNRA, we expect to enroll 3-4 participants per month to meet recruitment goals. Subjects will be required to participate for 2 days (intake, screening) + 2 weeks (formal experimental study), coming to the CNRA lab M, W, F.

Research data will be collected at scheduled time points during intake, baseline, experimental conditions, and end-of-study. Urine assays will assess recent cocaine use as urine benzoylecgonine < 300 ng/mL confirmation.

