Exclusion criteria will include: (1) current DSM-IV diagnosis of any psychoactive substance dependence other than cocaine, marijuana, or nicotine; (2) have a DSM-IV axis I psychiatric disorder or neurological disease or disorder requiring ongoing treatment and/or making study participation unsafe; (3) significant current suicidal or homicidal ideation; (4) medical conditions contraindicating administration of suvorexant (e.g., severe pulmonary disease, severe cardiovascular disease or clinically abnormal EEG, severe liver or kidney disease, seizure disorder, or sleep disorder – particularly narcolepsy); (5) taking medications known to have significant drug interactions with the study medication(s) (e.g., MAO inhibitors, anticonvulsants, haloperidol, phenothiazines, anesthetics, and all sedatives); (6) currently or recently (last 3 months) treated for substance use [other than cocaine or nicotine] or another psychiatric condition; (7) conditions of probation or parole requiring reports of drug use to officers of the court; (8) impending incarceration; (9) pregnant or nursing for female patients; (10) inability to read, write, or speak English [required for lab tasks and psychometric scales]; (11) unwillingness to sign a written informed consent form; (12) subjects with alcohol use disorders or are drinking > 7 alcoholic drinks per week. All subjects who are excluded will be given referral information to other local treatment programs.

E2. Sources of Materials.

We will obtain information about subjects from structured interview evaluations, physical examinations, self-report measures, and computerized behavioral tasks. This information will be collected at specified time points during the study phases of intake, baseline assessment, experimental testing, and end-of-study. The biological specimens obtained from all subjects will include urine, saliva for cortisol assessment, and breath samples for alcohol detection. Individuals who volunteer to participate will be assigned a subject number (e.g., 10500), under which all information collected will be filed. All materials will be obtained for the specific purposes of this research.

E3. Potential Risks

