Involvement of Individuals Currently Addicted to Drugs and/or Are Frequent Drug Abusers. We have taken into consideration the need to assess the participant's ability to provide informed consent (via use of screening and the Shipley-2 aptitude assessment). While these are non-treatment seeking individuals, a serious and concerted effort will be made to link these individuals to drug abuse treatment. At study end, subjects will receive a follow up medical examination and a session with a licensed counselor in our treatment research clinic, who will provide information about treatment options and referrals. As described thoroughly in D1, D2, E1 and E4 we have rigorous medical examination and screening procedures to assure the absence of any medical or mental condition for which further drug exposure would be contraindicated. Our procedures do not entail exposure to higher doses, rates of administration, or new route of administration than they would normally encounter by under usual circumstances. If subjects have participated in prior clinical drug intervention trials at our treatment research clinic, a complete list of drugs and dosing protocols will be reviewed and kept in his/her evaluation record. Subjects using any current CNS active medications will be excluding from testing and rescheduled (if medication use was idiosyncratic, e.g., OTC for recent cold or headache) or excluded (if medication use is regular or for a chronic condition). In particular, we will exclude those with alcohol use disorders or who report frequent alcohol consumption (> 7 time drinks per week), as suvorexant is contraindicated with alcohol due to potentially dangerous interactions with regard to sedative effects.

Administration of Drugs to Incarcerated Individuals. Individuals who are currently on parole or probation with random drug testing by court officers, or who are currently incarcerated, will be excluded

Administration of Drugs to Individuals with Mental Disorders. Individuals with DSM-IV Axis - I mental disorders other than SUD will be excluded.

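### The weekly alcohol exclusion is more than 10 drinks in Participants and setting but more than 7 in E1 and E10, and nothing says which governs

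*Combined protocol and SAP*

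**What the plan says.** Four places in the combined protocol and SAP give a weekly alcohol limit.

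- **Research Plan, Participants and setting:** "We will also exclude those individuals who are drinking > 10 alcoholic drinks per week". Beside it stands a reference level, "NIAAA criteria problem drinking = at least 14 drinks per week", and the sentence goes on "and who are unwilling to stop using alcohol in the evening for the two weeks of the study". The next sentence excludes binge drinkers, defined as 5 drinks for men or 4 for women in under 2.5 hours.
- **E1, narrative:** nearly the same paragraph, but with "drinking > 7 alcoholic drinks per week, and who are unwilling to stop using alcohol in the evening". It has no binge-drinking exclusion.
- **E1, numbered exclusion criterion 12:** "subjects with alcohol use disorders or are drinking > 7 alcoholic drinks per week". It mentions neither binge drinking nor evening drinking.
- **E10, paragraph on individuals currently addicted to drugs:** it excludes alcohol use disorder or "frequent alcohol consumption (> 7 time drinks per week", closing the bracket there.

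Two further places address alcohol use without a weekly number. E4 (Procedures to Minimize Drug-Related Risks) describes AUDIT and SCID screening for low alcohol risk, tells participants not to drink in the evening, and makes regular alcohol use a reason for stopping. E10 (Safety of Research Participants Outside of the Research Site) lists an exclusion for frequent regular use.

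The protocol's reason for restricting alcohol appears in Participants and setting, "because the study medication (suvorexant) is contraindicated with alcohol use", and in E10: "suvorexant is contraindicated with alcohol due to potentially dangerous interactions with regard to sedative effects". E3 adds that the drug's listed risks rise with alcohol.

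**The concern.** An eligibility limit should have one value. Here the main eligibility section of the Research Plan gives one figure, and the human-subjects text under the Data Safety Monitoring Plan heading gives another. The looser figure sits in the section that has the fuller alcohol text and is the only one with the binge-drinking rule, so it is a plausible source for a screening form.

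What is at stake is participant safety and consistent screening. The drug is taken at 10 PM and reaches 20 mg in week 2, the highest dose that E3 allows. E3 describes a dose-related risk of impaired alertness and lists compromised respiratory function and complex night-time behaviours among the precautions. Whether someone at 8 to 10 drinks per week may take the drug should not depend on which page the screener opened.

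**Working it through.** No sample-size or power formula applies. The check sets the rules side by side and asks who is treated differently.

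**Inputs.** Let d be whole drinks per week for a candidate who has no alcohol use disorder, does not binge drink, and will stop evening drinking. The rules on amount are:

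- Participants and setting: exclude if d > 10
- E1 narrative: exclude if d > 7
- E1 criterion 12: exclude if d > 7
- E10: exclude if d > 7

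For the first two, the amount and the unwillingness to stop evening drinking are read as two separate grounds for exclusion.

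**Result by range.**

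| d | Participants and setting | E1 narrative | Criterion 12 | E10 |
|---|---|---|---|---|
| 7 or fewer | admit | admit | admit | admit |
| 8, 9 or 10 | admit | exclude | exclude | exclude |
| 11 or more | exclude | exclude | exclude | exclude |

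The sections disagree on 10 − 7 = 3 whole-number values: 8, 9 and 10.

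**Which figure governs?** Nothing ranks one section above another, explains the difference, or labels either figure as replaced. Applied cumulatively, the combined rule is d > 10 or d > 7, which reduces to d > 7, so criterion 12 decides. The looser figure takes effect only if Participants and setting is used by itself.

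**Do the other safeguards settle it?** Only in part. The E4 screening and regular-use stop, and the E10 exclusion for frequent regular use, may catch some people at 8 to 10 drinks per week. Neither gives a weekly number, so neither chooses between 7 and 10.

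**Is the full alcohol rule in any one place?** No. Participants and setting has the binge rule but not the limit of 7. Criterion 12 has the limit of 7 but not the binge rule. A screener using either alone misses something.

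**The case against.** The strongest reply is that the conflict resolves itself. Exclusions accumulate, so a person barred by any one of them is out, and more than 7 controls. E4 and E10 refer to screening against the inclusion and exclusion criteria, and the only numbered exclusion list is the one in E1. Nothing says that staff would work from Participants and setting alone. This stands as a limit on the consequence: a protocol applied in full admits nobody at 8 to 10. It does not remove the inconsistency, because the cumulative reading is sensible but is not stated.

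A reader might also infer something stronger from the word 'and', which joins the amount to the unwillingness to stop evening drinking in Participants and setting and in the E1 narrative. Taken with strict literalness, both conditions would have to hold. A heavier drinker who agreed to avoid evening alcohol would then escape those two sections, and a lighter drinker who refused would be excluded by none of the four. The documents do not support treating this as what the plan provides. The sentence reads naturally as naming two excluded groups. Criterion 12 and E10 exclude on amount alone, which fits that reading. The strict reading would also set the E1 narrative against E1's own numbered list. What remains is a wording point, worth tidying while the figure is being corrected.

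**Conclusion.** The inconsistency is real: one section says more than 10 and three places say more than 7, with no rule for choosing. It affects candidates at 8, 9 or 10 drinks per week without alcohol use disorder or binge drinking, and only if screening relies on Participants and setting alone. That reliance is an assumption; the documents do not show that it happens. They also give no distribution of drinking among candidates, so the number of people affected cannot be estimated.

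The documents do not support inferring that such people will be enrolled or that the trial lacks alcohol safeguards. The alcohol use disorder exclusion appears beside both limits, and the E4 and E10 measures give partial protection. The binge rule cannot be counted as protection beside the stricter limit unless the sections are read together, because it appears only beside the looser one. Severity is minor. It is worth correcting because the protocol itself describes the interaction as potentially dangerous.

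**What to change.** 1. In Participants and setting, change the weekly limit to more than 7, the figure in the numbered criterion and the more protective one.
2. Add the binge-drinking exclusion to criterion 12, so that the weekly limit and the binge rule stand in one list.
3. As a wording clarification only, replace 'and' with 'or' before the evening-drinking condition in Participants and setting and in the E1 narrative, so that either condition clearly excludes.

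The cost is a few lines of amendment and possibly a slightly smaller eligible pool, by an amount that the documents do not allow to be derived. No change to the sample size or the analysis is needed.

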Novelty and promise of the orexin system. The orexins are a class of recently discovered amino acid peptides concentrated in the hypothalamus with projections widely distributed throughout the brain. Two orexin receptors (OXR1, OXR2) have been identified. The orexin system is neuromodulatory, increasing neural action potentials via the regulation of glutamate and GABA. Its primary role appears to be in *energy homeostasis* (e.g., arousal, vigilance). Accordingly, antagonism (blockade) of OXR1 and OXR2 promotes sleep^{39,40}. In addition, there is strong preclinical and phase 1 evidence that orexin antagonists modulate three key cocaine-related variables documented above: sleep^{39,40}, stress/anxiety⁴¹⁻⁴³, reactivity to stimulant drug cues, including cocaine⁴⁴⁻⁴⁷. Only one approved FDA compound with specificity for the orexin receptor system (**suvorexant**) is currently available in the US market. It is indicated for treatment of insomnia. We propose that, due to the ability to regulate stimulant drug-cue reactivity, anxiety/stress, and sleep, suvorexant is an intriguing and potentially efficacious compound for the prevention of relapse in CUD.

Summary. Medications that attenuate drug cue reactivity (attentional bias, craving), reduce stress/anxiety, and enhance sleep quality may be effective pharmacotherapeutics for SUD. As these three factors all contribute to relapse, orexin receptor antagonists may be ideally suited to address the dynamic interaction of these factors, thereby helping in the prevention of relapse.

[figure not shown]
Overall Aim. According to the conceptual model posited in Figure 1, the overarching aim of this project is to conduct a first-in-human drug user study to examine the effects of the orexin antagonist suvorexant on drug-cue reactivity and its interactions with stress/anxiety and sleep.

HYPOTHESES and SPECIFIC AIMS

1. **Main effect:** To characterize the direct effect of suvorexant on drug cue reactivity. We hypothesize that suvorexant will significantly attenuate cocaine cue reactivity (attentional bias, craving).
2. **Stress/anxiety interaction:** To characterize the degree to which stress/anxiety mediates the effect of suvorexant on drug cue reactivity. We hypothesize an indirect effect of suvorexant on drug cue reactivity via stress/anxiety, such that attenuation of cocaine cue reactivity (attentional bias, craving) will be greater in those with larger reductions in stress/anxiety duration.

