3. **Sleep interaction:** To characterize the degree to which sleep mediates the effect of suvorexant on drug cue reactivity. We hypothesize an indirect effect of suvorexant on drug cue reactivity via sleep, such that attenuation of cocaine cue reactivity (attentional bias, craving) will be greater in those with larger improvements in sleep duration.

*Conceptual Model:
Orexin System Effects on Relapse Risk*

Figure 1. Summary of Conceptual Model

Research Plan

Our group at the University of Texas Center for Neurobehavioral Research on Addiction (CNRA) has developed, utilized, and validated laboratory models of drug relapse, allowing us to examine pharmacotherapeutic and cognitive-behavioral interventions for relapse prevention.

Study design. To accomplish the project aims, we will utilize a mixed-model experimental design, with a between-groups factor of dose (suvorexant vs. placebo) and a within-subjects factor of time. Subjects will receive suvorexant (**10 mg week 1, 20 mg week 2**) or placebo PO, once daily at 10 PM. Medication condition will be double-blind, with urn-randomized assignment to dose condition balanced by gender and severity of cocaine use. A summary of timelines and measures is shown in the Table below.

Mon	Wed	Fri	Mon	Wed	Fri	Mon
1,4,5,6,7	1,2,3,4,5	1,2,3,4,5	1,2,3,4,5,6,7	1,2,3,4,5	1,2,3,4,5	1,2,3,4,5,6,7
Key: (1) Provide medication (MEMS bottle); (2) Compliance data for medication adherence (MEMS, pill count, riboflavin, text message); (3) Side effects data, med check, UA toxicology; (4) Sleep data; (5) stress /anxiety data; (6) acute stressor challenge (cold pressor); (7) Cue reactivity data						

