Data Analyses. We will use multilevel modeling to evaluate cue reactivity (attentional bias, craving) as a function of suvorexant, time, and the interaction of suvorexant x time. Hypothesis evaluation will utilize both Frequentist and Bayesian methods. Power and sample size focus on the effect of suvorexant on drug cue reactivity (AB, CCQ). From a Frequentist perspective, assuming a correlation of $r = 0.5$ between measurement points and $\alpha = 0.05$, a sample of $N=30$ participants will provide 80% power to detect a moderate effect (Cohen’s $f = .0.24$) for the interaction if treatment and time. For Bayesian analyses, multilevel priors will be vague and neutral: coefficients ~Normal (mean = 0, variance = 1×10^6), level 1 variance ~ Gamma (shape=.001, scale=.001), level 2 variances ~ Uniform (0,100). Frequentist statistical models will utilize traditional mediation analyses as recommended by Baron and Kenny⁶⁸, which permits unbiased OLS estimates appropriate for this experimental design and sample size⁶⁹, and which we have utilized in previous published research⁷⁰. Bayesian statistical models will utilize path analysis (BSEM) to evaluate the mediating effects of stress/anxiety (biological and subjective-rated) and sleep (biological and subject-rated) for the effects of suvorexant on drug cue reactivity. An example of a mediation analysis using Bayesian SEM may be found Arbuckle⁷¹. Uncertainty surrounding the Bayesian estimate for the indirect effect employs the posterior distribution of the parameter (i.e. the product coefficient): a density denoting the probability that different values of the parameter obtain given the observed data. This approach may be particularly important for evaluating more complex mediation models (e.g. multiple mediators, latent variables) in the context of small sample sizes. Use of the MCMC (Monte Carlo Markov Chain) approach in Bayesian analyses has demonstrated superior small sample performance relative to maximum likelihood-based approaches in continuous, normally distributed data⁷². These properties are likely due to the MCMC approach’s lack of reliance on large sample size assumptions⁷³. BSEM prior specification will adapt recommendations from Muthén and Asparouhov⁷⁴.

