Subject Payment. The payment schedule is detailed below. Subjects will be paid the medication compliance, study visit bonus, and participation earnings at the end of each experimental day (M, W, F). Subjects will receive an additional bonus (\$50) for completing of the study. Total possible payment for meeting all study requirements and collecting all bonus payments will be \$337.

Medication compliance. \$2 for each metric: 1) Medical Event Monitoring System (MEMS) bottle opening, (2) pill counts (empty bag), (3) positive riboflavin markers, and (4) text reply to reminder. Absence of each will result in payment not being earned for that specific metric. Total possible payment = \$8 per day X 14 study days = **\$112**. **Study visit bonus.** \$10 for on time arrival and providing an alcohol-free breath sample and urine sample. Total possible payment = \$10 per day X 7 visit days = **\$70**.

Participation. Total possible payment = \$15 per day X 7 visit days = **\$105**. **Completion bonus \$50**.

Subject participation requirements. Subjects must take the medication as close as possible to 10:00 PM each evening, and reply “yes” to the medication text prompt (texts will be sent at 15-minute intervals from 9:45 PM to 10:30 PM). On M, W, F over 2 consecutive weeks (see Study Design), subjects will visit the lab at 10 AM. At every visit, they will provide the following: medication update (MEMS bottle), side effects data questionnaire, med check up with nurse, UA fluorescence and toxicology, sleep data (wrist monitor and sleep questionnaire), and stress/anxiety questionnaires. The visit will take approximately 1 hour. In addition, on each Monday (day 1, 7, and 14) subjects will complete: (1) the cold pressor test (with cardiovascular measures and saliva sample for cortisol level), (2) the saccade-based attentional bias test, and (3) the cocaine cue reactivity questionnaire. On these three study days, the visit will take approximately 2 hours.

Data Safety Monitoring Plan

E1. Human Subjects Involvement and Participant Characteristics

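### The suvorexant x time test is valid, but using the pre-dose day-1 value as a covariate would give the same 2-df question more power at the plan's own r = 0.5

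*Combined protocol and SAP*

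**What the plan says.** The Data Analyses section evaluates "cue reactivity (attentional bias, craving) as a function of suvorexant, time, and the interaction of suvorexant x time". It mentions neither a baseline covariate nor a constraint that the arms share a day-1 mean. On sample size it says: "Power and sample size focus on the effect of suvorexant on drug cue reactivity (AB, CCQ". The power statement (N = 30, r = 0.5, alpha 0.05, Cohen's f read as 0.24, 80% power) is "for the interaction if treatment and time".

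Aim 1 is "To characterize the direct effect of suvorexant on drug cue reactivity" and is labelled the main effect.

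Under Subject participation requirements, "subjects will visit the lab at 10 AM", and the cue-reactivity tests fall on the three Mondays (days 1, 7 and 14). Under Study design, subjects take suvorexant or "placebo PO, once daily at 10 PM", with suvorexant given as "10 mg week 1, 20 mg week 2". The first cue-reactivity measurement therefore precedes the first dose. Assignment is randomized.

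**The concern.** Because assignment is randomized and day 1 is pre-dose, any day-1 difference between the arms is chance. Day 1 can therefore serve as a covariate. In the model as written it is one more outcome level, so the interaction tests arm differences in change from day 1. That subtracts the whole day-1 value, which is too much unless the measures correlate very highly across Mondays. With equal variances and r = 0.5, the best coefficient is 0.5.

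At stake is precision in a small trial. With 15 completers per arm, the planned test has 80% power only for effects of about 1 SD. The dose steps up between weeks, so the time course is uncertain. A 2-df test that covers several patterns is worth keeping, and the aim is to run it with less noise.

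**Working it through.** **Inputs.** From Data Analyses: N = 30, r = 0.5, alpha = 0.05, f = 0.24 and the model terms. From Subject participation requirements: three cue-reactivity days. Assumed, because the documents do not say: 15 per arm, equal correlation between Mondays, complete data and a two-sided test.

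**1. The plan's own figure.** For the within-between interaction with m time levels, lambda = N x m x f²/(1 − r).
- m = 3: 30 x 3 x 0.0576/0.5 = 10.37. With F(2,56), power is 0.808, so the stated 80% is right.
- m = 2, 4 and 7 give 0.718, 0.876 and 0.970. Only three levels fit, so day 1 is counted as an outcome level.

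**2. Effects that correspond to f = 0.24.** Let d be the vector of arm differences in SD. Then lambda = (30/4) x Σ(d − mean d)²/(1 − r), and f = 0.24 means Σ(d − mean d)² = 12 x 0.0576 = 0.691.
- Constant (0, d, d): d = 1.02.
- Linear build-up (0, d/2, d): d = 1.18 at day 14.
- Week 2 only (0, 0, d): d = 1.02.

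**3. Where the gain comes from.** At r = 0.5 the mean of days 7 and 14 has variance (1 + 0.5)/2 = 0.75. Subtracting day 1 gives 0.75 + 1 − 2 x 0.5 = 0.75. Regressing on day 1 gives 0.75 − 0.25 = 0.50. The day-7 versus day-14 contrast has the same variance either way. Under randomization both tests have the same null, no arm difference at days 7 and 14.

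**4. Adjusted 2-df test.** lambda = 7.5 x d'S⁻¹d/(1 + 1/26), where d now holds the day-7 and day-14 differences. S has variance 1 − r² = 0.75 and covariance r − r² = 0.25. The 1/26 is the cost of estimating the slope. With unstructured covariance the reference is F(2,26).

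| Pattern at f = 0.24 | d'S⁻¹d | lambda, planned | lambda, adjusted (before 1/26) | lambda, adjusted | Power, adjusted |
|---|---|---|---|---|---|
| Constant | 2d² | 10.37 | 15.55 | 14.98 | 0.915 |
| Build-up | 1.375d² | 10.37 | 14.26 | 13.73 | 0.888 |
| Week 2 only | 1.5d² | 10.37 | 11.66 | 11.23 | 0.815 |

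The planned test has power 0.808 with compound symmetry, F(2,56), or 0.783 with unstructured covariance, F(2,27). Simulation (40,000 trials) gave 0.914 / 0.890 / 0.814 for the adjusted test. Type I error was about 5% for both tests.

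**5. Effect detectable with 80% power (SD), N = 30, constant / build-up at day 14 / week 2 only.**

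| r | Planned, unstructured | Adjusted, unstructured |
|---|---|---|
| 0.3 | 1.23 / 1.42 / 1.23 | 0.92 / 1.13 / 1.14 |
| 0.5 | 1.04 / 1.20 / 1.04 | 0.87 / 1.045 / 1.00 |
| 0.7 | 0.81 / 0.93 / 0.81 | 0.73 / 0.87 / 0.80 |
| 0.8 | 0.66 / 0.76 / 0.66 | 0.62 / 0.73 / 0.66 |

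At r = 0.5 the reduction is about 17% / 13% / 4% with the same covariance for both tests. The planned test would need about 42 / 40 / 34 participants to match the adjusted one at 30. Against the compound-symmetric planned test (1.01 / 1.16 / 1.01), the reduction is about 14% / 10% / 1% and the matching N about 41 / 37 / 31.

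**The case against.** The planned test has the right size and delivers its stated power. The analysis paragraph is short, and it omits a covariate without ruling one out. This is therefore a choice between valid methods, and the gain is conditional in four ways.

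- **Time course.** For a week-2-only effect at r = 0.5, power goes only from 0.808 to 0.815. If the effects at days 7 and 14 had opposite signs, adjustment would lose, from 0.81 to about 0.76. That pattern contradicts the hypothesised attenuation.
- **Correlation.** The Measurements section calls eye movements "typically stable across repeated measures", so r for attentional bias may exceed 0.5. Against the compound-symmetric planned test, the adjusted test's detectable effect for week 2 only is slightly worse: 0.80 versus 0.78 SD at r = 0.7, and 0.66 versus 0.64 at r = 0.8.
- **Comparator.** The plan names no covariance structure, and its 80% matches compound symmetry. The smaller set of gains (14% / 10% / 1%) is the stricter comparison.
- **Coding of time.** The plan does not say whether time is categorical or linear. A linear 1-df interaction already has power 0.886 for the build-up pattern, so adjustment adds nothing there. For the other two patterns it has 0.783, and adjustment still helps.

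All of this stands as a limit on the size of the gain. None of it removes the gain for a sustained effect, which is present at every r examined from 0.3 to 0.8.

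**Conclusion.** The concern holds, as a matter of efficiency and not as an error. The plan uses a randomized, pre-dose baseline only as an outcome level. At its own r = 0.5 and f = 0.24, adjusting for that baseline raises power from 81% to about 92%, 89% or 82%, depending on the time course. This sets the planned test in its more favourable compound-symmetric form against the adjusted test with unstructured covariance. With unstructured covariance for both, the starting point is 78%. The gain is larger at lower r and fades at higher r. The documents give no correlation for either measure beyond the assumed 0.5. The figures rest on 15 completers per arm, equal correlation across Mondays and no missing data. That day 1 is an outcome level is inferred from the model terms and the reproduced power; the plan does not state it.

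**What to change.** In Data Analyses, state for attentional bias and the CCQ separately:

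> The two post-dose Mondays (days 7 and 14) are modelled by arm, Monday and arm x Monday, with the day-1 value of the same measure as covariate (slope free at each Monday) and unstructured covariance. The Aim 1 test is the joint 2-df test of the arm difference at these two Mondays. Each Monday's difference is reported with its interval. The unadjusted suvorexant x time interaction is secondary.

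The covariate form drops anyone without a day-1 value. If some are missing, a three-Monday model with a common day-1 mean for both arms answers the same question and keeps those participants; in a small sample with missing data the two forms agree only approximately. Use the same mean structure in the Bayesian multilevel model. In Aim 1, say that the main effect means the post-dose arm difference, not a group term averaged over the pre-dose visit.

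The unstructured covariance is deliberate. The compound-symmetric adjusted test with F(2,53) had a simulated type I error of 5.6%.

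The change needs no new visit, participant or measure. It costs about one residual degree of freedom, F(2,27) to F(2,26). If r is high and the effect appears only in week 2, it brings no gain, or a small loss against a compound-symmetric analysis.
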